7.4. MISSING DATA

Missing safety data will not be imputed unless otherwise specified. Missing efficacy data will be handled as described in Section 14.1.2, 14.2.2 and 14.3.2 of this analysis plan.

7.5. MULTIPLE COMPARISONS/ MULTIPLICITY

Primary and secondary endpoints will be analysed hierarchically, thus no multiplicity correction will be applied.

7.6. EXAMINATION OF SUBGROUPS

Subgroup analyses will be conducted as stated in the exploratory analysis sections. It should be noted that the study was not designed to detect treatment differences with high statistical power within subgroups.

The following subgroups will be assessed and described within the exploratory analysis sections:

- Prior use of anti-TNF treatment
 - o Yes
 - o No
- Duration of disease

Document:	x:\biostatistics\documentation\sap\pya18238_izana_izn-101	_sap_v1_0_2019050.docx	
Author:		Version Number:	1.0
		Version Date:	07May2019
Tomplete No :	CS TD DS016 Devision F	Deference: CC W/	DCOO

Template No.: CS_TP_BS016 Revision 5

Reference: CS_WI_BS00

Effective Date: 01Apr2018

1.0

07May2019

Reference: CS_WI_BS00

- \circ <2 years
- $\circ \geq 2$ years
- Gender:
 - Female
 - o Male

8. OUTPUT PRESENTATIONS

A separate template shows conventions for presentation of data in outputs.

The templates provided describe the presentations for this study and therefore the format and content of the summary tables, figures, and listings to be provided by IQVIA Biostatistics.

9. DISPOSITION AND WITHDRAWALS

All subjects who provide informed consent will be accounted for in this study.

Subject disposition, screen failures and withdrawals, and reasons for exclusion from each analysis sets will be presented for the ENR set. Protocol deviations, including inclusion and exclusion criteria will be presented for the RND set.

10. DEMOGRAPHIC AND OTHER BASELINE CHARACTERISTICS

Demographic data and other baseline characteristics will be presented, by randomised group and overall, for the FAS.

The following demographic and other baseline characteristics will be reported for this study and collected on the eCRF:

- Age (years) calculated relative to date of consent
- Duration of the disease
- Sex
- Race
- Ethnicity
- Baseline Weight (kg)
- Height (cm)

 Document:
 x:\biostatistics\documentation\sap\pya18238_izana_izn-101_sap_v1_0_2019050.docx

 Author:
 Version Number:

Template No.: CS_TP_BS016 Revision 5

Effective Date: 01Apr2018

Copyright © 2009, 2010, 2012, 2016, 2018 IQVIA. All rights reserved. The contents of this document are confidential and proprietary to IQVIA Holdings Inc. and its subsidiaries. Unauthorized use, disclosure or reproduction is strictly prohibited.

Version Date:

- BMI (kg/m^2)
- Prior use of anti-TNF treatment (stratification factor)

11. MEDICAL HISTORY

Medical History information will be presented for the FAS.

- Medical History will be coded using Medical Dictionary for Regulatory Activities (MedDRA) V. 21.0
 - Medical History conditions are defined as those collected in the medical history eCRF page.
 - Presented by SOC (System Organ Class) and PT (Preferred Term).

12. MEDICATIONS

Medications will be presented for the SAF and coded using WHO Drug Dictionary Version Dictionary B3 format version March 2018.

See 17 for handling of partial dates for medications, in the case where it is not possible to define a medication as prior, concomitant, or post treatment, the medication will be classified by the worst case; i.e. concomitant.

- 'Prior' medications are medications which started and stopped prior to the first dose of study medication.
- 'Concomitant' medications are medications which:
 - started prior to, on or after the first dose of study medication and started no later than 14 days following last dose of study medication,
 - AND ended on or after the date of first dose of study medication or were ongoing at the end of the study.
- 'Post' medications are medications which started more than 14 days following the last dose of study medication.
- Incidence of prior, concomitant and post medications will be presented by ATC Level 4 code and Preferred Term (PT).

Reference: CS WI BS00

Document:	x:\biostatistics\documentation\sap\pya18238_izana_ izn-101_sap_v1_0_2019050.docx		
Author:	Version Number:	1.0	
	Version Date:	07Mav2019	

Template No.: CS_TP_BS016 Revision 5

Effective Date: 01Apr2018

13. STUDY MEDICATION EXPOSURE

Exposure to study medication, expressed as number of subjects who received their 1st, 2nd, 3rd and 4th injections, and duration of exposure, will be presented for the SAF.

The date of first study medication administration will be taken from the eCRF "Subcutaneous dosing of IMP" form. The date of last study medication will be taken from the eCRF "End of Treatment" form.

Interruptions, compliance, and dose changes will not be taken into account for duration of exposure.

13.1. DERIVATIONS

Duration of exposure (days) = date of last study medication injection – date of first study medication injection+1.

14. EFFICACY ENDPOINTS

All efficacy data will be listed for all randomised subjects.

14.1. PRIMARY EFFICACY ENDPOINT

14.1.1. PRIMARY EFFICACY ENDPOINT AND DERIVATION

• Proportion of subjects who achieve an ASAS20 clinical response at Week 12

ASAS20 responder is defined as follow:

A subject with an improvement from baseline of at least 20% and an absolute improvement of at least 10 units on a 0-100 VAS in at least 3 of the following four domains collected on the eCRF and no worsening in the fourth domain (defined as a 20% increase from baseline and an absolute increase of 10 units):

- Subject's Global Assessment of Disease Status,
- Subject's Assessment of Spinal Pain,

 Document:
 x:\biostatistics\documentation\sap\pya18238_izana_izn-101_sap_v1_0_2019050.docx

 Author:
 Version Number:
 1.0

 Version Date:
 07May2019

Template No.: CS_TP_BS016 Revision 5

Effective Date: 01Apr2018

Copyright © 2009, 2010, 2012, 2016, 2018 IQVIA. All rights reserved. The contents of this document are confidential and proprietary to IQVIA Holdings Inc. and its subsidiaries. Unauthorized use, disclosure or reproduction is strictly prohibited.

Reference: CS WI BS00

- Function (overall BASFI score),
- Inflammation, (average of the last 2 questions of BASDAI: intensity of morning stiffness, duration of morning stiffness)

The data used to calculate ASAS20 are collected in the eCRF at Baseline and Week 12.

14.1.2. MISSING DATA METHODS FOR PRIMARY EFFICACY ENDPOINT

Subject with missing primary endpoint data (either at Baseline or Week 12) will be treated as non-responders.

14.1.3. PRIMARY ANALYSIS OF PRIMARY EFFICACY ENDPOINT

The primary objective of this study is to test the hypothesis that there is no difference in the ASAS20 responders proportion between the namilumab and the placebo group.

H₀: $\pi_{nam} = \pi_{pbo}$, where π represents the ASAS20 responder rate.

The primary endpoint ASAS20 will be assessed using a Bayesian analysis on the FAS. The control arm will have a beta prior with parameters rate = 0.3 and v = 20, and the namilumab arm will have a beta prior with rate 0.6 and v = 5. The parameterization used here is beta(α , β) where rate = α/v and $v=\alpha + \beta$, and the density of beta(α , β) is proportional to $x^{\alpha}(1-x)^{\beta}$. Posterior distributions will be calculated using simulation (100000 random draws). The parameter distributions (estimated rates and rates difference) and 5th, 10th, 25th, 50th, 75th, 90th, and 95th percentiles of the posterior distribution will also be presented graphically. Given the observed data, the posterior probability $\eta = P(\pi_{nam} > \pi_{pbo})$ will be calculated and presented. Values of $\eta > 0.927$ will provide strong evidence that namilumab exhibits therapeutic benefit relative to placebo control.

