The study will consist of a maximum 4-week Screening Period, followed by a 12-week double-blind treatment evaluation period, followed by a 16-week safety follow-up period, for a maximum study duration of approximately 32 weeks or 224 days per subject. Eligible subjects will be randomised on Day 1 of Week 0 and receive study treatment administered sc on Day 1 of Week 0, Week 2 (loading dose), Week 6 and Week 10. Subjects will return on Week 12 for an End of Treatment (EoT) visit during which efficacy and safety assessments will be performed. Subjects will have a follow-up visit 16 weeks after the EoT visit.

Number of Investigators and Study Centres:

Up to 10 Investigators and 10 study centres are expected to participate in this study.

Number of Subjects:

Approximately 70 subjects will be screened to achieve 42 subjects randomly assigned to study treatment (36 on active treatment and 6 on placebo) and 42 evaluable subjects for an estimated total of 36 evaluable subjects on the active treatment arm and 6 evaluable subjects in the placebo treatment arm.

Treatment Groups and Duration:

Test product, dose and mode of administration:

Namilumab 150 mg sc administered at Weeks 0, 2, 6 and 10.

Reference therapy, dose and mode of administration:

Matching placebo solution sc administered at Weeks 0, 2, 6 and 10.

Statistical Methods:

The primary endpoint will be ASAS20. Based on literature data, the prior for the placebo and namilumab groups will follow a beta distribution with mean of 0.3 and 0.6, respectively. Weighting for the priors will be equivalent to 20 and 5 subjects, respectively. Sample size is the smallest sample size so that P{ θ act > θ pbo| Y(HA)} >0.927 with probability 0.9, assuming true response rates of 0.3 and 0.6 for the control and namilumab arms, respectively. For a 6:1 randomisation, 42 patients need to be randomised.

Efficacy endpoints will be summarised by treatment group and visit. The posterior distribution of the primary endpoint will be computed using the conjugate priors, and the mean, standard deviation, and 5th, 10th, 25th, 50th, 75th, 90th, and 95th percentiles of the posterior distribution will be presented.

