9.0 STATISTICAL CONSIDERATIONS

9.1 Statistical Hypotheses

The hypothesis to be tested is H₀: $\pi_{nam} = \pi_{pbo}$, where π represents the ASAS20 rate. The hypothesis will be evaluated using a Bayesian analysis.

Prior clinical data in AS were used as the basis for prior distributions. Criteria for inclusion of studies were that the studies involved a similar biological agent, and were double-blind and placebo-controlled. Week 12 was the target visit and was used in the calculations for the priors, but for secukinumab Week 16 was used since Week 12 data were not reported outside of the figures.

Data for control groups are shown in Figure 2 and Table 7. The estimated sample-size weighted mean ASAS20 was 0.34. The secukinumab studies allowed for prior DMART and anti-TNF agents, which yielded a lower ASAS20 than the other studies.

Data for the active groups are shown in Figure 3 and Table 8. The estimated sample-size weighted mean ASAS20 was 0.6. As can be seen, a fair amount of variability is shown in the results with a secukinumab (75 mg) group with a low ASAS20 of 0.41, and tofacitinib (5 mg twice daily [BID]) with an ASAS20 of 0.81. The remaining studies exhibit ASAS20 tightly clustered around 0.6.

Based on these results, the prior for the control will be targeted to ASAS20 of 0.3, and the active ASAS20 to 0.6.

Control Prior Data

Figure 2 Estimated ASAS20 and 95% Confidence Intervals for Placebo Treatment Group Data

Secu = secukinumab.

Table 7 Reported ASAS20 Results for Placebo Treatment Group for Reference Studies

Compound	Reference	Week	Ν	ASAS20
Etanercept	Maksymowych (2015)	12	106	0.37
Golimumab	Sieper (2012, 2016) ACR	12	100	0.40
Tofacitinib	van der Heijde (2017)	12	51	0.41
Secukinumab (phase 2)	NCT00809159	12	6	0.17
Secukinumab	Baeten 2015; MEASURE 1	16	122	0.29
Secukinumab	Baeten 2015; MEASURE 2	16	74	0.28
Pooled			459	0.34

Active Prior Data

Figure 3 Estimated ASAS20 and 95% Confidence Intervals for Active Treatment Group Data

Secu = secukinumab (M.1 = MEASURE 1 study, M.2 = MEASURE 2 study); Tofa = tofacitinib; Goli = golimumab; Etan = etanercept; Certo = Certolizumab pegol.

Compound	Reference	Dose	Week	Ν	Value
Certolizumab pegol	Label	200 mg Q2weeks	12	65	0.57
Certolizumab pegol	Label	400 mg Q2weeks	12	56	0.64
Etanercept	Maksymowych (2015)	50 mg Q1week	12	101	0.52
Golimumab	Sieper (2012, 2016) ACR	Gol Q4weeks	12	97	0.71
Tofacitinib	van der Heijde (2017)	2 mg BID	12	52	0.52
Tofacitinib	van der Heijde (2017)	5 mg BID	12	52	0.81

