9.2 Sample Size Determination

The placebo prior = beta(p=0.3, n=20), and the prior for active is beta(p=0.6, n=5). The sample sizes are the smallest n such that the median Q(P{ $\theta_{act} > \theta_{pbo}$ | Y(H_A)}, 1 - γ) > Q(P{ $\theta_{act} > \theta_{pbo}$ | Y(H₀)}, γ), where Q(f, γ) represents the γ quantile from the distribution f, and Y(H_A) represents data generated under the alternative hypothesis, and Y(H₀) represents data generated under the null hypothesis. Sample sizes are shown in Table 9. The recommended sample size is 42 (6 on placebo, 36 on active). A plot of the distribution of P{ $\theta_{act} > \theta_{pbo}$ | Y} with both hypotheses overlapping as a function of the total sample size is shown in Figure 4.

Table 9 Sample Sizes for 6:1 Randomisation, Based on the Parameter y

γ	N Placebo	N Active	N Total
0.80	2	12	14
0.85	4	24	28
0.90	6	36	42

Figure 4Distribution of Posterior Probability $P(\theta_{act} > \theta_{pbo})$ as a Function of Total
Sample Size, Under Both Hypotheses

Shaded areas represent the middle 80% of the distribution (between the 10th and 90th percentiles).

9.3 **Populations for Analyses**

For purposes of analysis, the analysis sets in Table 10 are defined. For efficacy analyses, the Full Analysis Set (FAS) will be the primary analysis set, and the Per Protocol (PP) Analysis Set will be secondary. For safety analyses, the Safety Analysis Set will be the primary analysis set.

Analysis Set	Description		
Entered Analysis Set	All subjects who sign the ICF.		
Randomly Assigned to Study Treatment Analysis Set	All subjects in the Entered Analysis Set who are assigned to study treatment.		
Full Analysis Set	All subjects randomly assigned to study treatment and who take at least 1 dose of study treatment and have specific post-baseline assessments available.		
Per Protocol	All subjects in the Full Analysis Set that have week 10 efficacy data.		
Completer Analysis Set	All subjects in the Full Analysis Set who complete the study.		
Safety Analysis Set	All subjects randomly assigned to study treatment and who take at least 1 dose of study treatment. Subjects will be analysed according to the treatment they actually received.		

Table 10Analysis Sets

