9.4.1 Efficacy Analyses

Endpoint	Statistical Analysis Methods
Primary	The primary endpoint ASAS20 will be assessed using a Bayesian analysis. The control arm will have a beta prior with parameters rate = 0.3 and v = 20, and the namilumab arm will have a beta prior with rate 0.6 and v = 5. Posterior distributions will be calculated, and parameter distributions shown. The mean, standard deviation, and 5 th , 10 th , 25 th , 50 th , 75 th , 90 th , and 95 th percentiles of the posterior distribution will be presented. The posterior distribution will also be presented graphically. Given the observed data, the posterior probability $\eta \equiv P(\pi_{nam} > \pi_{pbo})$ will be calculated (Raineri 2014) and presented. Values of $\eta > 0.927$ will provide strong evidence that namilumab exhibits therapeutic benefit relative to placebo control. Missing data will be treated as non-responders for this analysis. For assessment of robustness of the analysis, the analysis will be performed on Completer Analysis Set.
Secondary	Summary statistics of ASAS20, ASAS40 and other efficacy endpoints will be summarised by visit
~ contain y	and treatment group. Summary statistics will be provided on both the Full and PP Analysis Sets.
Exploratory	Statistics used to summarise these endpoints will be described in the SAP.

Table 11Efficacy Analyses

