9.4.4 Missing Data

Data from subjects who withdraw from the study, including AEs and any follow-up, will be included in the analyses of primary and secondary outcomes.

Missing data (including those due to early discontinuations) will be imputed by a non-responder imputation (NRI). The NRI will be the primary imputation method for handling the missing data.

As a sensitivity analysis, the analysis will also be performed on completers only.

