14.1.4. SENSITIVITY ANALYSIS OF PRIMARY EFFICACY VARIABLE(S)

- Sensitivity to missing data assumptions
 - A sensitivity analysis imputing missing placebo subjects as Responders instead of Non-Responders will be performed.
- Sensitivity to adjustment for covariates

Document:	x:\biostatistics\documentation\sap\pya18238_izana_izn-101	_sap_v1_0_2019050.docx	
Author:		Version Number:	1.0
		Version Date:	07May2019
Template No.	CS_TP_BS016 Revision 5	Reference: CS_WI	_BS00

Effective Date: 01Apr2018

- A sensitivity analysis including the stratification as covariate will be performed.
- o Sensitivity to analysis set
 - The primary analysis will be repeated for the COM and PPAS analysis set.

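### The η > 0.927 rule leans on a placebo prior worth 20 subjects against 6 randomised, no planned sensitivity analysis varies a prior, and the placebo rate behind Table 9 is not the one stated

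*SAP*

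**What the plan says.** SAP 14.1.3 and Protocol 9.4.1 give the control arm a beta prior with rate 0.3 and weight 20, and namilumab one with rate 0.6 and weight 5. The Protocol synopsis expresses this in subjects: "Weighting for the priors will be equivalent to 20 and 5 subjects, respectively". Protocol 9.2 recommends 42 subjects, 6 on placebo and 36 on namilumab. The SAP then states that η = P(π_nam > π_pbo) above 0.927 "will provide strong evidence that namilumab exhibits therapeutic benefit relative to placebo control".

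On the historical placebo data, Protocol 9.1 reports: "The estimated sample-size weighted mean ASAS20 was 0.34". The prior is nevertheless centred at 0.3.

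On robustness, SAP 14.1.4 imputes missing placebo subjects as responders, adds the stratification factor as a covariate, and changes the analysis set: "The primary analysis will be repeated for the COM and PPAS analysis set". Protocol 9.4.1 has "For assessment of robustness of the analysis, the analysis will be performed on Completer Analysis Set", and Protocol 9.4.4 has "As a sensitivity analysis, the analysis will also be performed on completers only".

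On calibration, the synopsis derives the sample size "assuming true response rates of 0.3 and 0.6 for the control and namilumab arms, respectively". Protocol 9.2 says of Y(H0) only that it "represents data generated under the null hypothesis". The readable text gives no placebo rate for it, and Figure 4 is not shown.

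**The concern.** The prior supplies 20 of the 26 units of weight in the placebo posterior, so the comparator is mostly historical. Its centre lies below the protocol's own pooled rate, which favours namilumab. If the true placebo rate in this population is higher than the prior assumes, the rule becomes easier to meet without a drug effect.

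Nothing planned would show this. The covariate analysis has no stated model or priors. The Fisher exact test (SAP 14.2.3.1) covers secondary endpoints only, so Week 12 ASAS20 has no planned prior-free comparison. The Week 12 interim (SAP 4.2) uses the primary endpoint for strategic decisions, and any prior sensitivity analysis chosen after that unblinding would be post hoc.

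**Working it through.** **Inputs.** Priors Beta(6,14) and Beta(3,2), from rate = α/v with v = 20 and 5 (SAP 14.1.3, Protocol 9.2). Arms of 36 and 6, threshold 0.927, no missing data.

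**Formulas.** With i of 36 namilumab and j of 6 placebo responders, the posteriors are Beta(3+i, 38−i) and Beta(6+j, 20−j). Then η(i,j) = ∫ f_nam(x) F_pbo(x) dx. The probability of meeting the rule at true rates (p1, p0) is the sum of Bin(i; 36, p1) × Bin(j; 6, p0) over those of the 37 × 7 = 259 outcomes with η > 0.927. This is exact.

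**Reproducing the plan's figures.** Table 9 takes the smallest N for which the (1−γ) quantile of η under HA exceeds the γ quantile under H0. With active rate 0.6:

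| Placebo rate H0 / HA | N for γ = 0.80 / 0.85 / 0.90 | 90th percentile of η under H0, N = 42 |
|---|---|---|
| Protocol | 14 / 28 / 42 | 0.927 (threshold) |
| 0.30 / 0.30 | 14 / 21 / 28 | 0.888 |
| 0.34 / 0.30 | 14 / 21 / 35 | 0.9267 |
| 0.35 / 0.30 | 14 / 28 / 42 | 0.933 |
| 0.33 / 0.33 | 14 / 28 / 42 | 0.9215 |
| 0.34 / 0.34 | 14 / 28 / 42 | 0.9267 |

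Of the rates tried, only 0.34 to 0.345 in both hypotheses match both Table 9 and 0.927. The synopsis criterion agrees. At 0.3/0.6, N = 35 already reaches P(η > 0.927) = 0.9002, so 42 is not the smallest N. At 0.34/0.6, N = 35 gives 0.881 and N = 42 gives 0.907.

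**Weight of the prior.** 20/26 = 77% prior and 6/26 = 23% trial. With no data at all, the two priors give η = 0.897.

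**Chance of meeting the rule with equal true rates.** 0.30: 4.1%. 0.34: 8.6%. 0.35: 10.0%. 0.40: 19.4%. The choice γ = 0.90 implies about 10%.

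**Range in Table 7.** Secukinumab rows: (6×0.17 + 122×0.29 + 74×0.28)/202 = 57.12/202 = 0.283, where the rule is met in 2.8%. The other three rows: (106×0.37 + 100×0.40 + 51×0.41)/257 = 100.13/257 = 0.390, where it is met in 17.2%.

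**Single outcomes.** For 21/36 (58%) against 4/6 (67%), the planned posteriors are Beta(24,17) and Beta(10,16), with means 24/41 = 0.585 and 10/26 = 0.385, and η = 0.949. Flat priors give Beta(22,16) and Beta(5,3), with means 0.579 and 0.625, and η = 0.388. The rule is therefore met although the observed namilumab rate is the lower one. For 17/36 against 2/6, the smallest passing count with two placebo responders, planned η is 0.933. It becomes 0.819 with the control centred at 0.39, 0.895 with the placebo weight halved and 0.710 with flat priors.

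**Chance of exceeding 0.927 at true 0.6/0.3.** Planned priors 92.6%; control Beta(7.8,12.2) 73.9%; control Beta(3,7) 82.8%; flat priors in both arms 46.2%.

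**The case against.** The priors are pre-specified and sourced, and a weight of 20 is a heavy discount of 459 historical placebo subjects. This is a phase 2a proof-of-concept study. Protocol 9.1 links the lower secukinumab rates to prior treatment including anti-TNF agents. This trial allows up to 50% anti-TNF inadequate responders or intolerant subjects, so a placebo rate between the two groups of studies is plausible. At their midpoint, (0.283 + 0.390)/2 = 0.336, the rule is met in 8.0%. If the threshold was calibrated at 0.34, it already allows for a prior centred too low. Results near the design rates are robust: 22/36 against 2/6 gives η = 0.993 as planned, 0.971 with the control centred at 0.39 and 0.981 with half weight. Only flat priors (0.890) miss the bar. Observed rates by arm are planned, and η can be recomputed from two counts.

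All of this stands, and it rules out stronger readings. A reader might infer that the rule has an inflated error rate. The documents set no type I error limit, and the rate stays below the 10% implied by γ = 0.90 at both 0.30 and 0.34. A reader might also infer from the 21/36 against 4/6 example that the rule often favours a worse-performing arm. By the same enumeration, meeting the rule with a lower observed namilumab rate has probability about 0.02% at a common rate of 0.34 and 0.3% at 0.40. The example shows how the rule works, not how often this happens. Nor is 42 shown to be wrong, since it follows from a placebo rate of 0.34.

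The objection does not supply a pre-specified check of the prior. A reader's own recalculation is not a planned analysis.

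**Conclusion.** The point holds as an omission that should be fixed, not as an error in the primary analysis. The rule's false-positive rate is acceptable at the rates the protocol treats as likely (4.1% at 0.30, 8.6% at 0.34) and exceeds 10% only above 0.35, reaching 19.4% at 0.40. Six placebo subjects cannot establish which rate applies, and no planned analysis shows whether a borderline success survives another reasonable placebo prior. Separately, the stated rates do not reproduce Table 9. The calibration rate appears to be the pooled 0.34, but that is inferred from the match, and Figure 4 might state it.

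The figures assume Beta(6,14) and Beta(3,2). SAP 14.1.3 also gives a density proportional to x^α(1−x)^β, which read literally means Beta(7,15) and Beta(4,3). The false-positive rate at 0.34 would then be 7.4%, and 17/36 against 2/6 would give 0.923 and miss the bar. The conclusion is the same, but the two statements conflict.

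**What to change.** Keep the primary priors, threshold and sample size.

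1. Before the Week 12 interim unblinding, add a 'Sensitivity to prior' item to SAP 14.1.4. Recompute η on the FAS with the control centred at 0.39, Beta(7.8,12.2), and with the placebo weight halved, Beta(3,7), each with Beta(3,2) for namilumab. Show Beta(1,1) in both arms as a descriptive reference only. Report these beside the primary η and the observed rate in each arm. If the 0.927 conclusion changes under either of the first two, say so and name the prior.
2. In Protocol 9.2 and the synopsis (or SAP 14.1.3 if the protocol is not amended), state the placebo rate actually used for Table 9 and 0.927, and the rule's false-positive rates at 0.30, 0.34 and 0.40.
3. Correct the density in SAP 14.1.3 to match the stated rate and weight, x^(α−1)(1−x)^(β−1).

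The cost is a few lines of text and code, with no more subjects. The downside is that about 21% of planned successes at true rates 0.6/0.3 would be reported as dependent on the placebo prior, against about 86% of false positives at 0.34. A failure becomes a success in only one outcome, 13/36 against 0/6 with half weight. The flat prior stays descriptive because, on its own, it would change the conclusion for 50% of planned successes at 0.6/0.3, which mainly reflects the small placebo arm.
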